Finally, cluster randomized controlled trials are the gold standard to compare health services and policy interventions, but significant inputs in time and resources are usually required rendering this study design impractical in program settings. However, as we propose in this project, when many cases are easily available (index cases reported through passive surveillance), existing infrastructure is in place (the current

surveillance team), and the outcome measures can be feasibly measured (incidence will be collected through routine case reporting data, with secondary outcomes measures mainly collected through minimal follow-up visits), a cluster randomized controlled trial can be performed quickly and efficiently.

3 Study aims

The **overall objective** of this proposal is to critically evaluate TPE vs. RACD as a surveillance and response strategy for malaria elimination.

Our **primary aim** is to:

Compare the impact of TPE versus RACD on incidence of malaria cases. We will test the hypothesis that TPE compared to RACD will result in a lower cumulative incidence.

In addition, the following **secondary aims** will be addressed:

Effectiveness:

1. To compare the impact of TPE versus RACD on seroprevalence. We will test the hypothesis that TPE, compared to RACD, will result in lower exposure to malaria, as assessed by antibodies to antigenic markers of recent exposure near the end of the study period (expected mid 2017).
2. To compare the impact of TPE versus RACD on prevalence of infection. We will test the hypothesis that TPE, compared to RACD, will be more effective in decreasing the prevalence of infection near the end of the study period (expected mid 2017).
3. To compare the impact of TPE versus RACD on the proportion of imported incident cases. We will test the hypothesis that TPE compared to RACD will result in a higher proportion of imported incident cases.
4. To compare the impact of TPE versus RACD on time to first incident local case subsequent to the intervention. We will test the hypothesis that TPE compared to RACD will result in a longer time to the first incident local case.
5. To compare the impact of TPE versus RACD on transmission potential, measured by relatedness of strains by microsatellite genotyping. We will test the hypothesis strains detected in TPE versus RACD are less related to ancestor infections.

Feasibility:

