14.2 Outcome measures

Table 6. Outcome measures

Outcome	Indicator
Primary Aim	
Incidence	Cumulative incidence of all cases (Pf infection) identified by passive surveillance in the locality subsequent to the first reported case during the study period (not including additional cases found through RACD). Cases include both locally acquired and imported infections.
Secondary aims (effectiveness)	
Exposure (seroprevalence)	Seroprevalence to markers of recent exposure using ELISA in end-line survey samples taken from residents in Target Areas near the end of the study (expected mid 2017), excluding index cases detected through passive surveillance.
Infection prevalence	Prevalence of infection by LAMP and QTNASBA testing for gametocytes in LAMP positives in end-line survey samples taken from residents in Target Areas near the end of the study (expected mid 2017), including index cases detected through passive surveillance.
Time to first local post-intervention incident case	Time to first incident local case in the Target Area subsequent to the intervention. Target Areas that receive a repeat intervention will qualify to be included again at subsequent interventions.
Proportion of imported incident cases	Proportion of imported incident cases in the locality subsequent to the first reported case will be measured through passive surveillance. Additional cases found through RACD will not be included.
Transmission potential (by genotyping)	Microsatellite genotyping will be performed on samples collected from index cases as well as secondary cases.
Secondary aims (feasibility)	
Coverage	Proportion of persons residing within approximately 200m (TPE localities) or 500m (RACD localities) of the index case who consented to participate in the study and who completed the initial procedures for their study arm (finger prick for RDT in the RACD arm, initial dose of DP in the TPE arm)
Adherence	Proportion of persons who completed 3 days of therapy among all individuals initiated on DP in the TPE arm, as assessed by pill count
Prevalence of SAEs related to treatment	Proportion of subjects experiencing SAEs deemed possibly, probably, or definitely related to DP or AL, out of the total number of subjects enrolled
Acceptability	Qualitative assessment (See Section 10)
Cost	Cost per index case-level intervention, cost per case averted.

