Cement block or brick

Plaster

No observation conducted

42. *Observe:* What is the roof primarily comprised of?

Grass or palm

Metal sheets or tile

No observation conducted

43. *Observe:* Does the structure where the person sleeps have windows? Yes No

If yes, observe: Are the windows screened or covered? Yes No

44. *Observe:* Are there cracks/spaces at the eaves of the structure? Yes No

45. *Ask:* Has this home be sprayed in the past year? Yes No Don't Know

If yes, ask to see spray card to confirm house has been sprayed.

Spray card confirmed

No spray card

Cannot find spray card

If yes, were all the houses sprayed? Yes No Don't Know

If yes, do you sleep under a sprayed structure? Yes No Don't Know

46. *Ask:* Does your household own a bed net? Yes No

If yes, ask: How many bed nets do you have in the household? _____

How many are treated with insecticide? _____

Did you sleep under your bed net anytime within the past week? Yes No

If yes, ask: Is your bed net treated with insecticide? Yes No Don't Know

If no, ask: Why didn't you sleep under a bed net within the past week?

Too hot

- Too cold
- Used by someone else
- Net not hung up
- Net worn out/poor condition
- Net dirt
- Net bad for health
- Don't like shape or color
- Other _____

47. Are there any water bodies around or near the house? Yes No Don't Know

If yes, ask: what kind of body of water (check all that apply):

- river lake reservoir pond other, specify: _____

If yes, ask: What is the closest distance to a water body?

- <50m 50-99m 100-499m 500m-999m ≥1 km

Thank you for our participation in this study.

48. As mentioned, we would like to return in 6-9 months to check on the resolution of your infection. We would also like to return in mid 2017 to check on whether there continues to be malaria in your community; at this visit we would like to collection in your family and neighbours in addition to you. Each visit will only take a few minutes. Your participation in these follow-up studies will be voluntary. Are you willing to be contacted for these follow-up visits?

- Yes No Don't Know

49. Case Investigation Comments: Is there any other information that is relevant for this case investigation?

Case Determination *(To be conducted by supervisors following completion of investigation)*

50. *Origin of infection*

- Local
- Imported from another country
- Imported from another area of Swaziland
- Unknown
- Other

51. *Case epidemiology*

- Index
- Secondary case from RACD

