- Secondary case but identified in health facility
- Unknown
- Other

Response Determination *(To be conducted by supervisors following completion of investigation)*

52. *Please check all that apply regarding the response:*

- Receptive area –TPE study locality

- TPE planned
- TPE not planned as already completed in the past 8 weeks, note aciid: _____ and patient name _____

- Receptive area: RACD study locality
 - RACD planned
 - RACD not planned as already completed in the past 5 weeks, note aciid: _____ and patient name _____

- Receptive area: Non-Study locality
 - RACD planned
 - RACD not planned as already completed in the past 5 weeks, note aciid: _____ and patient name _____
 - Imported Network screening planned
 - Other, explain _____

- Non -receptive area
 - Imported Network screening planned
 - RACD planned, explain why _____
 - Other, explain _____

53. Response comments

54. Determination conducted by _____

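### Two secondary outcomes appear to rest on a local/imported label assigned by supervisors who also record the study arm, with no decision rule or masking stated

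*Combined protocol and SAP*

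**What the plan says.** Appendix C (case investigation form) ends with two blocks, Case Determination and Response Determination. Both carry the instruction "To be conducted by supervisors following completion of investigation". In the first, item 50 ("Origin of infection") offers local, imported from abroad, imported from elsewhere in Swaziland, unknown, and other. No rule for choosing among them is printed. In the second, item 52 records whether the locality is TPE or RACD and whether a recent intervention makes a new one unnecessary, for example "TPE not planned as already completed in the past 8 weeks". A single line, item 54, records who made the determination.

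Table 6 (section 14.2) has two secondary effectiveness outcomes that need an origin:
- "Proportion of imported incident cases in the locality subsequent to the first reported case will be measured through passive surveillance"
- "Time to first incident local case in the Target Area subsequent to the intervention"

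The expected direction is stated in section 3, aim 3: "We will test the hypothesis that TPE compared to RACD will result in a higher proportion of imported incident cases". Aim 4 expects a longer time to the first local case under TPE. Section 9.4 also describes the imported share as a surrogate for the reproduction number under control.

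For the primary outcome, Table 6 says: "Cases include both locally acquired and imported infections".

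**The concern.** The trial is open-label, and the role that assigns origin also writes down the arm. A case with a clear travel history, or clearly none, leaves little room for judgement. A case with some travel or an incomplete history leaves more, and the protocol states which answer is expected in which arm.

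Recording a local TPE case as imported moves both outcomes towards TPE: it raises the imported share and removes an event from the time to first local case. If the two outcomes agreed, that would be weaker support than it looks, because they share one label.

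A second gap exists even if nobody is influenced by arm. The plan does not say whether importation from elsewhere in Swaziland, unknown and other count as imported, count as local, or are left out.

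**Working it through.** **Does the label feed the outcomes?** Table 6 names no form item. It says that the imported share comes from passive surveillance, and item 50 is the only place in the visible forms where origin is recorded. The dependence is therefore a reasonable inference, not a statement in the plan. For time to first case the text is split. Table 6 and aim 4 specify a *local* case, while the analysis text (section 14.4, secondary analysis 4) speaks of an index case and an incident infection, without *local*. Origin matters under Table 6 and aim 4, and not under the analysis text.

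**Is there a safeguard elsewhere?** Section 4.3 separates roles only for generating the randomization. Section 4.2 says that genotyping cases from outside the study localities should sharpen the local/imported classification. It does not say who applies the result, whether they know the arm, or whether it can change item 50.

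**How large could the effect be?**

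Inputs:
- Table 2 totals, Sept 2012 to March 2015: 236 local, 97 imported, 333 in all. Summing the 63 localities with at least one case reproduces all three totals.
- Baseline imported share p = 97/333 = 0.291.
- Share m of truly local TPE cases recorded as imported: 5%, 10%, 20%. These are assumptions; the documents give no error rate. Relabelling is taken to occur in TPE only and in one direction, with no true difference between arms.

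Formulas:
- Observed TPE imported share = p + (1 − p)m.
- If local cases arise at a constant rate and each is recorded as local with probability 1 − m, the apparent hazard ratio for a recorded local case is 1 − m.

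| m | TPE imported share | Shift | Apparent hazard ratio, local cases |
|---|---|---|---|
| 0 | 29.1% | 0 | 1.00 |
| 5% | 0.291 + 0.709 × 0.05 = 32.7% | +3.5 points | 0.95 |
| 10% | 0.291 + 0.709 × 0.10 = 36.2% | +7.1 points | 0.90 |
| 20% | 0.291 + 0.709 × 0.20 = 43.3% | +14.2 points | 0.80 |

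For scale, a true halving of local cases from the same baseline gives 97/(97 + 118) = 97/215 = 45.1%, a rise of 16 points.

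**Sensitivity to the baseline.** The shift in imported share is (1 − p)m, so it shrinks as p rises. Section 1.1 reports imported shares of 51% and 71% in earlier seasons, apparently for the whole country. With m = 10%, the shift is 0.49 × 0.10 = 4.9 points at 51% and 0.29 × 0.10 = 2.9 points at 71%. At 71%, a true halving of local cases gives 0.71/(0.71 + 0.145) = 83.0%, a rise of 12.0 points. Table 2 is the closer match to the study localities. The hazard ratio of 1 − m does not depend on p.

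**The case against.** The strongest reply has five parts.

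- *The main result is safe.* This stands for the primary outcome as Table 6 defines it. Section 9.4 does list incidence of local cases among the data collected, so the two sections should be aligned to keep it that way. Table 9 gives no power result for either affected outcome.
- *Silence is not absence.* A reader might infer that no rule is planned. The documents do not show that. Section 13.1 promises standard operating procedures for all project activities, section 18 lists one for data analysis, and part of Appendix C is missing from the visible text. The supportable statement is that no rule or masking is stated.
- *Origin is not pure judgement.* The form collects dated overnight stays for the past 8 weeks (item 35), and genotyping is planned with classification as a stated purpose. Both narrow the room for bias. Neither is tied to item 50 by a rule.
- *Nothing shows that supervisors lean towards TPE.* A reader might infer that the two outcomes are biased. The form shows only that the opportunity exists. Section 4.2 adds that local and imported cases can both trigger the intervention, so origin does not decide whether a response takes place.
- *The size is assumed.* Comparing 7 points with 16 invites the claim that relabelling could mimic nearly half of a real effect. That comparison needs 10% of all local TPE cases to be moved, in one arm and one direction, at a 29% baseline. If only 20% of local cases had any travel (also an assumption), half of those would have to be misassigned. The documents support none of these rates.

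**Conclusion.** The point holds as a limited one. Two secondary effectiveness outcomes appear to use an origin label assigned by a role that also records arm, and the visible text states neither a decision rule nor masking. Time to first case is affected only under the wording of Table 6 and aim 4. The primary outcome in Table 6 is unaffected.

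Under the assumed relabelling of 5%, 10% or 20%, the TPE imported share would be about 33%, 36% or 43% against 29%, and the apparent hazard ratio for local cases about 0.95, 0.90 or 0.80, with no true effect. The shift in share is smaller if the baseline imported share is higher. These figures show sensitivity; they do not estimate a bias. The change is worth making because it is cheap and uses travel data that the form already collects.

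**What to change.** For trial outcomes:

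1. Write down, before analysis, a rule that derives origin from items 34 and 35 (travel place and dates against the 8-week window), and run it on data without arm or locality.
2. State how importation from elsewhere in Swaziland, unknown and other are counted, and how the genotyping in section 4.2 enters, including whether it can override the travel-based result. Apply it without knowledge of arm.
3. Let existing staff settle the cases that the rule cannot, from a record stripped of arm, home locality, GPS coordinates and item 52. Removing item 52 alone would not be enough, because locality determines arm.
4. Keep the supervisors' item 50 for programme response, and use it as a sensitivity analysis.
5. Reconcile section 14.4, secondary analysis 4, with Table 6 on whether the event is a *local* case, and section 9.4 with Table 6 on which cases count as incidence.

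Cost: one written rule, a script and some redaction of records; no new field data. Downsides: the trial label may differ from the programme label for some cases, and work or travel places left in a redacted record may still hint at the locality. History-taking in the field stays unmasked, so the change fixes the classification step and not the collection of travel data.

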Appendix D. Unsuccessful Case Investigation

(Malaria Cases table)

1. Malaria Case ID (Scan Barcode) _____

Investigation Details

2. Investigation date |__|__|/|__|__|/|__|__|
date month year

3. Investigation conducted by, (check all that apply)

[name] [name] [name] [name] [name] [name] [name]
 [name] [name] [name] [name] [name] Other _____

4. Conducted at

Homestead of case
 Work place of case
 Health facility where case presented
 Health facility where patient currently admitted
 NMCP
 Other _____

5. GPS coordinates of home (if subject's home visited)

Latitude: _____ Longitude: _____

Case Report (data available on immediate notification form)

6. Date Case Reported |__|__|/|__|__|/|__|__|
date month year

7. Case Identified by:

977 Hotline (If yes, EPR case ID # _____)
 Active Case Detection
 Quality Assurance Program
 Health facility site visit
 Phone Call to NMCP
 Other _____

Presentation at Health Facility (data available from immediate notification form or health facility worker)

8. Health Facility Name _____ not applicable

9. Presentation Date |__|__|/|__|__|/|__|__| not applicable
date month year

10. Disease severity Uncomplicated Severe Unknown

Patient Details

11. Patient Name: _____

12. Age: ___ years ___ months

13. Gender: Male Female Unknown

14. Contact Number _____

15. Name of household head if any _____

16. Region _____ Inkhundla _____ Locality _____

17. Reason case investigation was unsuccessful, check reason that best describes the situation:

Not reported
 No SMS notification
 Contact information is incomplete, inaccurate, not updated
 Not reachable by phone
 Not able to locate home
 Patient is not available (at work, busy etc.)
 Patient has left the country
 Patient resides here but is currently staying elsewhere (within Swaziland)
 Patient has since moved
 Refused
 Patient died
 House physically inaccessible
 Transport limitations

Quiz to assess participant's understanding of the study (to be given at time of TPE intervention visit only)

If the participant does not answer at least 4 out of the 5 questions correctly, the study team should reread the consent form and reassess the participant's understanding again. The study team should ensure that the participant is able to answer question 3 correctly, and re-explain how DP should be taken and given to child(ren).

1. Is participation in this study voluntary?

Appendix G: Neighborhood Information

Index case ID (aciid): _____

Neighborhood ID: _____

(NOTE This is a unique ID automatically generated by the tablet. If the same neighborhood has multiple interventions at different time points, it will receive a neighborhood ID with each episode)

Response determination:

- Study area- RACD
- Study area – TPE
- Non study area- RACD

Visit 1: Date and Time of arrival

Date: _____ (dd/mm/yyyy)
Time of arrival: ____: ____ (hh:mm)
Time of departure: ____: ____ (hh:mm)
Result code: _____

Visit 2: Date and Time of arrival

Date: _____ (dd/mm/yyyy)
Time of arrival: ____: ____ (hh:mm)
Time of departure: ____: ____ (hh:mm)
Result code: _____

Visit 3: Date and Time of arrival

Date: _____ (dd/mm/yyyy)
Time of arrival: ____: ____ (hh:mm)
Time of departure: ____: ____ (hh:mm)
Result code: _____

RESULT CODES:

- (1) COMPLETED, 100% of individuals within 200m & at least 30 individuals enrolled (stayed within 200m) (TPE localities only)
- (2) COMPLETED, 100% of individuals within 200m & at least 30 individuals enrolled (went beyond 200m) (TPE localities only)
- (3) COMPLETED, <100% of individuals within 200m but at least 30 individuals enrolled & 3 visits completed (stayed within 200m) (TPE localities only)
- (4) COMPLETED, <100% of individuals within 200m but at least 30 individuals enrolled & 3 visits completed (went beyond 200m) (TPE localities only)
- (5) COMPLETED, 100% of individuals within 500m & at least 30 individuals enrolled (RACD localities only)
- (6) COMPLETED, <100% of individuals within 500m but at least 30 individuals enrolled & 3 visits completed (RACD localities only)
- (7) INCOMPLETE with plans to return
- (8) INCOMPLETE with no plans to return
- (88) OTHER (SPECIFY) _____

Appendix H. Household level RACD questionnaire

Complete for all households (including households of the index case and households where no one is home or there is no consenting adult available). If this household has previously participated in RACD, a new Household level RACD questionnaire should still be completed.

Screen Type: Mass Screen Fever Screen

Neighborhood ID: _____

Index case ID (aciid): _____

Automatically generated by the tablet based on index case GPS coordinates. If GPS coordinates within the same 500 m radius as previously implemented index case investigation then assign same Neighborhood ID. Make sure automated number is unique for all tablets.

Surveillance Agent assigns barcode number to index case

Visit 1: Date: _____ (YY/MM/DD) Time of arrival: ____: ____ (hh:mm AM/PM)

Visit 2: Date: _____ (YY/MM/DD) Time of arrival: ____: ____ (hh:mm AM/PM)

Visit 3: Date: _____ (YY/MM/DD) Time of arrival: ____: ____ (hh:mm AM/PM)

For Visit 1, Date and Time captured automatically when household level questionnaire is saved. There should be 3 date fields, First Entered, Last Modified and Final Entered. On first visit same date is saved on all 3 fields.

For Visit 2, Last Modified and Final Entered should be modified to reflect that day's date and time, this should be done on the Individual level questionnaire and not the household level questionnaire unless edits were made to the household level questionnaire.

For Visit 3, Final entered should be modified to reflect that day's date and time, this should be done on the Individual level questionnaire and not the household level questionnaire unless edits were made to the household level questionnaire.

RACD Household Information

- Household ID (automatically generated by tablet) _____
Automatically generated by tablet and should be unique for all tablets to prevent duplication
- Household description (if household not a residential premise e.g. Church, describe here) _____
- GPS Coordinates
Latitude: _____
Longitude: _____
Automatically captured by tablet when household level questionnaire is saved, allow functionality to edit GPS coordinates by Agents
- Surveillance Agent Name, check all that apply
 [name] [name] [name] [name] [name] [name] [name]
 [name] [name] [name] [name] [name] Other _____
- Is household abandoned? Yes No
If Yes, continue to next question.
If No, close and save questionnaire.
- Is a consenting adult available? Yes No
If Yes, continue to next question.
If No, please indicate number of household members if known ____ (based on neighbor report, otherwise default is "999") and skip to end of questionnaire and move to next home.
999 denotes unknown number of households members
- Has this home been sprayed in the past year? Yes No Don't Know
If yes, ask to see spray card to confirm house has been sprayed.
 Spray card confirmed
 No spray card
 Cannot find spray card
If yes, we're all the houses sprayed? Yes No Don't Know
If yes, do you sleep under a sprayed structure? Yes No Don't Know
- Has this household previously participated in RACD before (during this TPE study period)?
 Yes No Don't Know
If yes, how many times before? ____
If yes, indicate month(s) and year(s) of all previous RACD interventions during this TPE study period
 - _____ (dd/mm/yyyy)
 - _____ (dd/mm/yyyy)
 - _____ (dd/mm/yyyy)

8. List individuals in the household:

	Household head? (check if yes)	Index case? (check if yes)	Name	Scan Barcode	Gender	Date of birth	Present (yes/no)	Notes (why person not present at home and best time to return to speak with person)	Consent obtained for questionnaire (yes/no/not yet)	Consent obtained for blood collection today (yes/no)	Agreed to be contacted for acceptability study (yes/no/ <18 yo, not applicable)	If subject refused blood collection, indicate if refuser survey administered (yes/no)
1.												
2.												
Etc.												

Note: Surveillance Agent to assign a barcode even if individual is not present

RACD Household level Dashboard (automatically generated)

	Barcode	Name	Household head? (check if yes)	Index case? (check if yes)	Gender	Age	Consent obtained for questionnaire (yes/no/not yet)	Consent obtained for blood collection today (yes/no)	Blood testing completed (yes/no)	RACD Questionnaire completed (yes/no)	Refuser Questionnaire completed (yes/no)	Notes	
1.													Edit
2.													Edit
3.													Edit
													Add Individual

Editable table listing all household members rising in a household, when a Surveillance Agent clicks on the 'Edit' button they will be shown the questionnaire below to insert information on additional questions not previously posed. When RACD questionnaire for household member is completed the table should refresh and 'Yes' should appear under column for RACD Questionnaire completed and other fields that have since been completed.

RACD Neighborhood Dashboard (automatically generated and includes missed homes)

Note: Use outlined boxes for the "30" criteria

House-hold number	Home of the index case, check if yes	Name of Household head	# of individuals eligible for participation	# of individuals reached (informed consent performed)	# of individuals providing consent for questionnaire	# of questionnaires completed	# of individuals providing consent for initial blood testing	# of individuals RDT performed	# of individuals DBS collected	# of individuals RDT positive	# of RDT+ individuals microtainer collected	# of individuals RDT+ referred for treatment
Totals:												

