7.1 Household-level questionnaire

A household will be defined as any single permanent or semi-permanent dwelling structure acting as the primary residence for a person or group of people that generally cook and eat together. Some households may include members who sleep in other dwelling structures within the same compound, if the members are still dependent on the head of household in the main household. A household resident will be defined as any person who has spent at least one night in the household in the past 5 weeks.

For each household enrolled in the study, a brief questionnaire will be conducted with the acting household head. The purpose of this questionnaire will be to determine household size and obtain information about the household structure as well as coverage of vector control interventions. If certain individuals are not present, the questionnaire will also aim to schedule a more suitable time to reach absent individuals. Separate questionnaires will be used for the RACD and TPE arms. The RACD household level questionnaire will collect blood testing results. The TPE questionnaire will collect information about doses of drugs administered (Appendix K).

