Appendix J. Household level TPE questionnaire

Complete for all households (including households of the index case and households where no one is home or there is no consenting adult available). Note, in the event that this household has already previously participated in TPE, a new Household level TPE questionnaire should still be completed.

Neighborhood ID: _____

Automatically generated by the tablet based on index case GPS coordinates. If GPS coordinates within the same 200 m radius as previously implemented index case investigation then assign same Neighborhood ID. Make sure automated number is unique for all tablets.

Index case ID (aciid): _____

Surveillance Agent assigns barcode number to index case

Visit 1: Date: _____ (YY/MM/DD) Time of arrival: ____: ____ (hh:mm AM/PM)

Visit 2: Date: _____ (YY/MM/DD) Time of arrival: ____: ____ (hh:mm AM/PM)

Visit 3: Date: _____ (YY/MM/DD) Time of arrival: ____: ____ (hh:mm AM/PM)

For Visit 1, Date and Time captured automatically when household level questionnaire is saved. There should be 3 date fields, First Entered, Last Modified and Final Entered. On first visit same date is saved on all 3 fields.

For Visit 2, Last Modified and Final Entered should be modified to reflect that day's date and time, this should be done on the Individual level questionnaire and not the household level questionnaire unless edits were made to the household level questionnaire.

For Visit 3, Final entered should be modified to reflect that day's date and time, this should be done on the Individual level questionnaire and not the household level questionnaire unless edits were made to the household level questionnaire.

TPE Household Information

9. Household ID (automatically generated by tablet) _____

Automatically generated by tablet and should be unique for all tablets to prevent duplication

10. Household description (if household not a residential premise e.g. Church, describe here) _____

11. GPS Coordinates

Latitude: _____

Longitude: _____

Automatically captured by tablet when household level questionnaire is saved, allow functionality to edit GPS coordinates by Agents

12. Surveillance Agent Name, check all that apply

[name] [name] [name] [name] [name] [name] [name]
 [name] [name] [name] [name] [name] Other _____

13. Is household abandoned? Yes No

If Yes, continue to next question.

If No, close and save questionnaire.

14. Is a consenting adult available? Yes No

If Yes, continue to next question.

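### In both household forms (Appendices H and J) the skip after the abandoned-household item is reversed; followed as printed, occupied homes would close before the member roster

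*Combined protocol and SAP*

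**What the plan says.** Appendix H, the RACD household form, asks "Is household abandoned? Yes No". The instruction for a positive answer is "If Yes, continue to next question"; for a negative answer it is "If No, close and save questionnaire". Appendix J, the TPE household form, carries the same item ("13. Is household abandoned? Yes No") with the same two instructions in the same order.

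The header of Appendix H says who the form is for: "Complete for all households (including households of the index case and households where no one is home or there is no consenting adult available". Appendix J opens in the same way. Section 7.1 gives the reason for the form: "The purpose of this questionnaire will be to determine household size and obtain information about the household structure", together with vector control coverage and arrangements for reaching absent members.

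In both forms the items that serve those purposes come after the skip. They are the consenting-adult item, with its fallback for homes where no adult is available ("If No, please indicate number of household members if known"), then spray status, previous participation, and the roster ("8. List individuals in the household"). Staff assign a barcode to each person at the roster, including people who are absent.

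**The concern.** No reading of the question makes the printed order sensible. A home that is not abandoned is the one to be enumerated, and the form closes it. A home that is abandoned is the one to be set aside, and the form goes on to ask whether an adult there can consent.

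The pages also serve as a tablet specification: they prescribe automatically generated identifiers, automatic GPS capture, self-populating fields and automatic dashboards. A skip rule in such a specification may be coded as it stands. Both arms carry the same reversal, so comparing one form with the other would not expose it.

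Two secondary outcomes are at stake. Coverage (Table 6) is a proportion of the people living within the target radius, and section 3 sets 80% as the TPE hypothesis. Refusal rates (section 10.2, Aim 1) are compared between arms. Both need a count of the people in each home, including those who were absent or declined.

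**Working it through.** This is a check of form logic. The plan states no figure for it, so there is none to reproduce.

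**Step 1: follow each kind of home through the form.** The trace is the same in Appendices H and J.

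| Home | Answer | Printed branch | What is recorded as printed | With the branches swapped |
|---|---|---|---|---|
| Occupied, adult present | No | Close and save | Household ID, description, agent; GPS on saving | Goes on to spray status and roster |
| Occupied, no adult available | No | Close and save | The same; size from neighbours is never asked | Size from neighbours, or 999 |
| Abandoned | Yes | Continue | Consenting-adult item answered No; size if known, otherwise 999 | Closes and leaves the denominator |

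As printed, the first two rows lose the list of persons. The third row can enter an empty home as a missed home of unknown size.

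**Step 2: see what depends on the roster.**

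- Individual forms (Appendices I and K) are opened from the household dashboard and filled with the barcode already assigned at the roster.
- A refusal recorded at the consent item of the individual form triggers the refuser survey, which is also keyed to that barcode (Appendix V).
- The neighborhood dashboards are generated automatically. They hold the number eligible and, by arm, the number with an RDT performed or a first dose received.

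A home closed before the roster therefore has no eligible count, no consent or refusal status, and no ordinary route to recording a test or a dose. The numerator of coverage is blocked as well as the denominator.

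**Step 3: ask whether another form could supply the counts.** Appendix G records visit dates, times and a result code. The codes say whether all or fewer than all individuals in the radius were reached, and whether at least 30 were enrolled. They hold no counts, so a coverage proportion cannot be rebuilt from them.

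**Step 4: see why the resident count matters.** Section 4.4 gives a mean of 32 people screened per index case and an estimated 53 residents within 200m, the latter based on data about missing individuals. Coverage to date follows as 32 / 53 = 0.604, the 60% stated there. Without a count that includes the people missed, the 53 has no counterpart in the trial data.

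**Step 5: check the 30-person rule.** Section 6.2 sends the team to further houses when, at the third visit, fewer than 30 people are enrolled, meaning that they have taken part in the intervention. The trigger is the number enrolled. It is affected only because individual records are reached through the roster.

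**Step 6: check the primary outcome.** Table 6 and section 9.4 take incidence from passive surveillance by locality. No household form feeds it.

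**The case against.** The strongest reply is that this is a slip that would correct itself. The header and section 7.1 make the intention plain, and the item that follows a Yes makes no sense for an abandoned home. Built literally, the form would close at the first occupied home visited, and staff could not open individual records in the ordinary way. That is an immediate failure in the field, not a silent bias found at analysis. Section 13.1 plans training on questionnaires and tablets and SOPs for all activities, and section 18 lists database check-ins. The programme had already estimated residents and coverage under RACD, although the documents do not show that it used this form. The household dashboards also offer a control for adding an individual, though nothing says that it replaces the roster once a form is closed.

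Most of this stands. It lowers the likelihood of loss but does not make the printed rule right.

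Three stronger readings are tempting and are not supported:

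- A reader might infer that every occupied household will go unenumerated. That is the literal branch, not a forecast. Household ID, description and agent also come before the skip, and GPS is captured on saving, so the household itself would still be recorded.
- A reader might infer that the tablet is wrong. The deployed logic is not in the documents.
- A reader might infer that the resident denominator decides whether a team goes beyond 200m. Section 6.2 uses the number enrolled, and the extension beyond 200m belongs to the TPE arm (section 4.4). The dashboards do outline the eligible total alongside the tested or treated total for the 30-person criterion, but the stated trigger is enrolment.

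**Conclusion.** The skip rule is wrong as written in both household forms. It is an internal inconsistency, since nothing suggests that anyone chose this order as a matter of design.

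If the forms are used or programmed as printed, occupied homes close before household size, spray status and the roster. The counts and barcodes behind coverage and refusal rates, and the enrolled count for the 30-person rule, would then not be captured. Whether that would happen cannot be settled from the documents, so no expected data loss can be given.

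The severity is low. The outcomes concerned are secondary, and section 2 already says that the trial is not powered for the coverage comparison between arms. The primary incidence outcome and every power figure are unchanged. The conclusion rests only on the printed wording, which is complete and identical in both appendices, and on the order of items within each form.

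**What to change.** In Appendices H and J, exchange the two branches after the abandoned-household item: Yes closes and saves, No continues. Then verify that the deployed tablet logic follows the corrected order, with one occupied and one abandoned test household in each arm's form. If the build is already right, only the text needs correcting.

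The cost is two words in each form and a short tablet check. No outcome definition, analysis or sample size changes.
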